3.4. Analysis Sets

Subjects who are taken to the procedure room for implantation will comprise the study population evaluated for the study objectives and associated endpoints.

The analysis sets are further defined as follows:

- **Safety Set (Attempted Implant):** The safety set includes all subjects who are brought into the procedure room for implantation.
- **Device Success/ Hemodynamic Performance Set (Implanted):** The device success/ hemodynamic performance set includes all subjects who are implanted with the Evolut R TAV, defined as the Evolut R TAV is placed in the aortic annulus and completely released from the EnVeo R catheter delivery system.

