2.7.4 Analysis of Clinical Data

Subjects who are taken to the procedure room for implantation will comprise the study population evaluated for the study objectives and associated endpoints.

The analysis sets are further defined as follows:

1. **Safety Set.** The safety set includes all subjects who are brought into the procedure room for implantation.
2. **Device Success/ Hemodynamic Performance Set.** The device success/ hemodynamic performance set includes all subjects who are implanted with the Evolut R TAV, defined as the Evolut R TAV is placed in the aortic annulus and completely released from the EnVeo R catheter delivery system.

The Final Report will be prepared when all patients have completed their follow-up evaluations or exited the study. All analyses will be described in a Statistical Analysis Plan (SAP) which will be completed prior to analysis. No interim analysis is planned.

Every effort will be undertaken to minimize missing data. A minimal amount of missing data is anticipated for the primary endpoint. However, if outcome data are missing, the primary analysis will be based on the complete case. And the Kaplan-Meier rate at 30 days and its standard error, as a secondary analysis, will be used in the calculation of the test statistic. To assess the potential impact of these missing data, a sensitivity analysis will be conducted which will include a complete case, a best case (assume missing subjects are alive), a worst-case (assume missing subjects have died), and a tipping point analysis.

Descriptive statistics will be provided for baseline demographic and clinical variables, as well as for the secondary endpoints. For categorical variables the numbers and percentages will be displayed. For

continuous variables the means, medians, standard deviations, and ranges will be presented. For time to event variables, Kaplan-Meier event rates and confidence intervals will be calculated.

No statistical techniques will be used to impute missing data for continuous or categorical outcomes. If a subject's data are missing for any reason, that subject will not be included in that portion of the analysis. The number of subjects included in each analysis will be reported so that the reader can assess the potential impact of missing data.

Additional (annual) reports providing only descriptive statistics will only be written upon request of the EC/IRB and/or Regulatory Authority, as applicable.

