3.7.1.4. Data Collection and Analysis Methods

The components of device success will be determined as follows:

- No death event occurs within 30 days post-procedure, or on or before the discharge date (if the discharge date is longer than 30 days post-procedure);
- In the implant CRF, the answer to “Was a single Evolut R deployed in the proper anatomical location?” should be “YES”;
- The criteria for ECHO will be based on the ECHO Core Lab Data for the time interval “Discharge”:
 - Absence of patient-prosthesis-mismatch
 - For subjects with BMI < 30 kg/m², index effective orifice area (EOAi) > 0.85 cm²/m²
 - For subjects with BMI ≥ 30 kg/m², index effective orifice area (EOAi) > 0.70 cm²/m²
 - BMI = weight(kg)/(height (m))², where weight and height are recorded on the ECHO CORE LAB form
 - Mean aortic gradient < 20 mmHg or peak velocity < 3 m/sec;
 - Absence of moderate or severe prosthetic valve regurgitation. Total Aortic Prosthetic Regurgitation on the ECHO CORE LAB form not equal to moderate or severe.

All of the above components must be satisfied to count as a device success. If any of the above components fails, the endpoint will be counted as a failure.

For the overall device success rate, the numerator will be the number of subjects whose procedures result in device success as described above, and the denominator will be the number of subjects whose device success results are not missing (either success or failure). Note that this analysis excludes those subjects with a missing response to any of the above five components (eg, the field “Post-implant Severity of Total Aortic Regurgitation”=“Unable to Assess” or “Not Recorded”, missing mean aortic gradient, or missing peak velocity, etc.) and without a “NO” response to any

of the components. In addition to the device success rate, the 95% C.I. will also be provided. This objective will be analyzed for the implanted analysis set defined in section 3.4.

3.7.2.Secondary Objective #2 (Efficacy) - Hemodynamic Performance

This objective is to characterize the hemodynamic performance at 24 hours to 7 days (discharge) and 1 year post procedure.

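### Device success is rated only among implanted subjects, so attempts that fail before or outside implantation leave the denominator instead of counting as failures; a supportive per-attempt rate should be added

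*SAP*

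**What the plan says.** SAP 3.4 and protocol 2.7.4 open with the same general statement: "Subjects who are taken to the procedure room for implantation will comprise the study population evaluated for the study objectives and associated endpoints". Each then defines two sets. The safety set takes everyone brought into the procedure room. The second set is narrower. In the protocol, "The device success/ hemodynamic performance set includes all subjects who are implanted with the Evolut R TAV". Both documents explain implantation in the same terms; in the SAP it is "defined as the Evolut R TAV is placed in the aortic annulus and completely released from the EnVeo R catheter delivery system".

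SAP 3.7.1.4 builds the rate on the second set:

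- Numerator: "For the overall device success rate, the numerator will be the number of subjects whose procedures result in device success".
- Denominator: "the denominator will be the number of subjects whose device success results are not missing".
- Scoring: "If any of the above components fails, the endpoint will be counted as a failure".
- Population: "This objective will be analyzed for the implanted analysis set defined in section 3.4".

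The components are procedural survival, correct siting of one valve, and three echo criteria (mismatch, gradient or velocity, regurgitation). SAP 3.7.1.4 reads the first as no death by day 30, or by discharge if that is later, and the second from an item on the implant form.

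The documents foresee attempts that do not end in an implant. Protocol 5.2.3 defines them, and Table 5 in protocol 5.4.4 gives them their own exit route with Implant, Discharge and 30 Day e-CRFs. Appendix E.2 defines ectopic deployment. Neither document plans a device success rate in the safety set.

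**The concern.** Membership of the analysis set depends on events that the endpoint is meant to score. A subject who dies on day 20 after an implant is in the set and is a failure. A subject who dies in the procedure room before release is not in the set at all. The same holds when no Evolut R is delivered, or when the only valve comes to rest outside the annulus: the siting component cannot be met, yet the attempt is removed and not scored.

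Device success is the first-listed secondary efficacy endpoint of a study whose purpose is to document device performance in routine practice. For that purpose, the chance that an attempt succeeds is a natural quantity to want, and the planned output does not supply it. The number analysed, which SAP 3.3 promises for each analysis, does not by itself separate attempts without implant from implanted subjects with unusable echo.

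**Working it through.** **The plan's own figure.** There is none to reproduce. SAP 3.7.1.2 states that no sample size was calculated for this objective, and neither document gives an expected device success rate or a number of attempts without implant.

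**Who is left out.** Setting the set definition beside the components:

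| Course of the attempt | In the implanted set? | Component result |
|---|---|---|
| Valve released in annulus, second valve needed | Yes | Fails siting of one valve; counted as failure |
| Valve released in annulus, death by day 30 | Yes | Fails survival; counted as failure |
| Death before release | No | Fails survival and siting; not counted |
| No Evolut R delivered | No | Fails siting; not counted |
| Only valve outside the annulus | No | Fails siting; not counted |

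**Direction of this exclusion taken alone.** Let E be the evaluable implanted subjects, S the successes among them, s = S/E, and k the attempts in the last three rows.

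- Planned rate: S/E = s.
- Per-attempt rate, same successes: S/(E + k).
- Shift: S/E - S/(E + k) = s x k/(E + k), which is never negative and is zero when k = 0.

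**Size, illustration only.** E = 1000 takes the planned number of implants (SAP 2) and assumes that all are evaluable. The values of s and k are assumptions. Shift in percentage points:

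| s | k = 5 | k = 10 | k = 20 | k = 30 |
|---|---|---|---|---|
| 80% | 0.40 | 0.79 | 1.57 | 2.33 |
| 90% | 0.45 | 0.89 | 1.76 | 2.62 |
| 95% | 0.47 | 0.94 | 1.86 | 2.77 |

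For example, 0.90 x 20/1020 = 1.76 points, so a planned rate of 90.0% corresponds to 900/1020 = 88.2% per attempt. With E = 900 and s = 90%, k = 5 and k = 20 give 0.50 and 1.96 points.

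**Scale.** At s = 90% and E = 1000 the half-width of the 95% confidence interval is h = 1.96 x sqrt(0.9 x 0.1/1000) = 1.86 points. The shift equals h at k = hE/(s - h) = 18.6/0.8814 = about 21 attempts.

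**The case against.** The strongest reply is that this is a choice of estimand, declared in advance. Protocol and SAP agree, the general population sentence is followed at once by the two set definitions, and the study is sized and capped on implanted subjects. The endpoint is descriptive, with no test and no performance goal. Deaths and 30-day safety events in subjects without an implant are counted, because the primary and safety analyses use the safety set (SAP 3.6.5 and 3.7.3.4). All of this stands. What it does not cover is a failure to deliver a valve that produces no death or safety event, and it supplies no per-attempt rate.

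A reader might infer three stronger things that the documents do not support.

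- *That the two documents conflict, or that the narrowing is hidden.* They match, and the set is named where the rate is defined.
- *That calling the rate overall presents it as a rate over all attempts.* In SAP 3.7.1.4 the word follows the list of components, and it more naturally means the composite as against its parts.
- *That the reported rate will, on balance, be too high.* This does not follow, because of a separate rule: "Note that this analysis excludes those subjects with a missing response to any of the above five components", unless another component has already failed. If echoes are missing independently of outcome, that rule pulls the rate down. Assume 1000 implanted, 900 true successes, 100 failures of which 50 show without echo, and k = 20, so that the full-data per-attempt rate is 900/1020 = 88.2%. With 15% of echoes missing the planned rate is 765/857.5 = 89.2%; with 30% missing it is 630/715 = 88.1%.

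The same example limits the remedy. Among evaluable subjects the per-attempt rate is 765/877.5 = 87.2% at 15% missing, no closer to 88.2% than the planned rate, and 630/735 = 85.7% at 30%, which is further away. A per-attempt rate removes the selection on the outcome but does not repair missing echo data. It is therefore supportive only, and the two sources of exclusion need to be counted apart.

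Echoes do need an implanted valve. That justifies the implanted set for the hemodynamic metrics. It does not justify it for device success, where a failed component already settles the result without an echo.

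**Conclusion.** The point holds in a limited form. The device success set is defined partly by the outcome, and attempts that fail the endpoint's own components are removed from the denominator. No per-attempt rate is planned. This follows from the text and needs no assumption.

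Taken alone, the exclusion raises the rate or leaves it unchanged. Its size cannot be found from the documents. The 0.45 to 1.76 points quoted for 5 to 20 such attempts assume 90% success and 1000 evaluable implants, are not upper bounds, and fall to zero if every attempt ends in an implant. No claim is made about the net direction of the reported rate, which also depends on missing echoes. No hypothesis test, error rate or power is affected. It is an inexpensive improvement to a descriptive endpoint, not an error that threatens the study's conclusions.

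**What to change.** In SAP 3.7.1.4:

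- Keep the planned rate and state beside it that it applies among implanted subjects.
- Add a supportive device success rate in the safety (attempted implant) set. Every attempted subject who does not end with one Evolut R released in its proper location counts as a failure, whether or not an echo exists. Implanted subjects are scored as now.
- Report the number attempted but not implanted, with reasons. Some may be procedures stopped before the device was introduced, and the reasons let a reader judge those.
- Report separately the number of implanted subjects whose echo could not be evaluated.
- Leave the hemodynamic metrics on the implanted set.

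Protocol 2.7 already provides for departures from its statistical section to be described and justified in the final report. Bounds for missing echo are an optional, separate matter.

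The cost is one SAP revision, an extra table row with two counts, and a second figure that is slightly less favourable than the first. Table 5 already requires the e-CRFs for these subjects. Whether the Implant e-CRF records why and when a procedure stopped must be checked, since the form is not among the documents.

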3.5. Kaplan-Meier Analyses

In the Kaplan-Meier analysis, the product-limit estimate of the event rate, the number of subjects at risk, the number of subjects with events, the Peto standard error of the estimate, and the loglog transformed 95% confidence interval using the Peto standard error at 1 month (30 days), 1 year (365 days), 2 years (730 days) and 3 years (1095 days) will be presented.

For subjects without an event, the date of censoring will be the latest date of all follow-up visits, assessments, and events (including death in those objectives where death is not the endpoint).

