3.6.3. Rational for Choice of Hypothesis

The performance goal for all-cause mortality at 30 days was established through the following data sources:

- Data from the CoreValve IDE clinical study
- Review of the published literature on the Medtronic CoreValve System current through April 2013

Criteria for selection of the articles included the following:

- Study was published in peer reviewed journal
- Study was multi-center
- Results were representative of high or above risk population
- Results for all-cause mortality were reported by device type
- Study was not a first in man, feasibility, or confined to early Medtronic CoreValve experience

Of the literature reviewed, 4 articles were selected. Information on the historical data is presented in Table 1.

Table 1 Information on Control Data Sources for Primary Safety Endpoint

Author	Study Name	Number of CoreValve Patients	Age (years) Mean \pm SD	Logistic Euroscore (%) Mean \pm SD	STS Score (%) Mean \pm SD	All-Cause Mortality at 30 days (%)
US CoreValve IDE study: Extreme Risk Cohort ¹		639	83 \pm 8	23 \pm 17	10 \pm 6	9.1
US CoreValve IDE study: High Risk Cohort ¹		390	83 \pm 7	18 \pm 13	7 \pm 3	3.3
Bosmans	Belgian Registry	141	82 \pm 6	25 \pm 15	Not reported	11
Gilard	FRANCE 2 Registry	1043	82 \pm 7	21 \pm 14	14 \pm 11	9.4
Chieffo	PRAGMATIC	453	81 \pm 7	21 \pm 13	8 \pm 6	7.5
Moat	UK TAVI Registry	452	81 \pm 7	18 (11-28)	Not reported	5.8
Random effects meta-analytic rate						7.3
						(95% CI 5.4 - 10.0)

1. Data include all access routes.

The random effect meta-analysis showed that the all-cause mortality rate at 30 days post procedure for CoreValve was 7.3% with a 95% C.I. of 5.4% to 10.0%. We expect Evolut R TAV will have a similar rate as CoreValve, which is 7.3% at 30 days. And the all-cause mortality rate for Evolut R will not be higher than the upper bond of the 95% C.I. for CoreValve. Therefore the performance goal was set to 10.0%.

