3.7.3.4. Data Collection and Analysis Methods

The CEC codes for the VARC-2 Combined Safety Endpoint:

- All-cause mortality (CEC Death Form)
- All stroke (disabling and non-disabling) (CEC: 102 to 107)
- Life-threatening bleeding (CEC: 110)
- Acute kidney injury: stage 2 or 3 (including renal replacement therapy) (CEC: 114 to 115)

- Coronary artery obstruction requiring intervention (CEC: 152)
- Major vascular complication (CEC: 120 to 127)
- Valve-related dysfunction requiring repeat procedure (BAV, TAVI, or SAVR)
 - Catheter intervention to repair or replace Evolut R
 - Surgery intervention on Evolut R

As described in section 3.5, a Kaplan-Meier analysis will be performed for the VARC-2 Combined Safety Endpoint at 30 days post-procedure and for each individual component. These objectives will be analyzed for the safety analysis set defined in section 3.4.

3.7.4. Secondary Objective #5 (Safety) - Event Rate of New Permanent Pacemaker Implant at 30 Days

This objective is to characterize the event rate of new permanent pacemaker implant at 30 days.

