3.7.4.3. Endpoint Definition

The endpoint is the KM event rate of new permanent pacemaker implant at 30 days post-procedure.

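### Kaplan-Meier with censoring at death slightly overstates the 30-day rates of the individual safety components and new pacemaker; cumulative incidence would estimate what the protocol asks for

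*SAP*

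**What the plan says.** SAP 3.5 sets the censoring date of a subject without an event as the latest date among visits, assessments and events, "including death in those objectives where death is not the endpoint". For any endpoint other than death, a subject who dies event-free is therefore censored at death.

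SAP 3.7.3.4 uses this method for early safety: "a Kaplan-Meier analysis will be performed for the VARC-2 Combined Safety Endpoint at 30 days post-procedure and for each individual component". Apart from all-cause mortality, the components are stroke, life-threatening bleeding, stage 2 or 3 acute kidney injury, coronary obstruction requiring intervention, major vascular complication, and valve dysfunction requiring a repeat procedure. SAP 3.7.4.3 builds the method into the pacemaker endpoint: "The endpoint is the KM event rate of new permanent pacemaker implant at 30 days post-procedure".

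The output in SAP 3.5 includes "the number of subjects at risk, the number of subjects with events", with results "at 1 month (30 days), 1 year (365 days), 2 years (730 days) and 3 years (1095 days) will be presented". Protocol 2.7.4 also plans Kaplan-Meier rates for time-to-event variables. Neither document mentions competing risks or cumulative incidence.

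Protocol 2.2.3 defines these endpoints as rates at 30 days after the procedure. SAP 3.7.3.1 and 3.7.4.1 make the objectives descriptive, without a test.

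**The concern.** A dead patient cannot later have a stroke or receive a pacemaker, so death is not ordinary loss to follow-up. Censoring it makes one minus Kaplan-Meier estimate the event risk in a hypothetical population where nobody dies. The protocol asks how often treated patients have the event by day 30, which is the cumulative incidence.

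The plan itself expects appreciable early mortality: "We expect Evolut R TAV will have a similar rate as CoreValve, which is 7.3% at 30 days". SAP 3.6.6 expects little missing data for the primary endpoint, so death could be a main reason for censoring before day 30. Death also counts as an event in the composite but as censoring in the other components. The component and pacemaker rates are results that the study exists to document, and SAP section 1 applies the plan to both the final report and the main manuscript.

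**Working it through.** **Plan figures.** The SAP gives no expected rate or sample size for these endpoints, so there is no figure of its own to reproduce. The one sized endpoint is 30-day mortality. Its N of 934 reproduces: exact one-sided binomial test, critical value 78 deaths, alpha 0.0493, power 0.9009. It does not depend on the Kaplan-Meier rule.

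**Inputs.** From SAP 3.6.3: 30-day mortality D = 7.3% ("was 7.3% with a 95% C.I. of 5.4% to 10.0"%), and a source range of 3.3% to 11%. Assumed: true event rates of 3%, 5%, 10% and 20%, and the timing of events and deaths.

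**Formulas.** Cumulative death hazard to day 30: Λd = −ln(1 − 0.073) = 0.0758. With cumulative event hazard Λe and death censored, 1 − KM = 1 − exp(−Λe). If both hazards are constant over the same interval, the cumulative incidence is CIF = Λe/(Λe + Λd) × [1 − exp(−(Λe + Λd))]. In each case Λe is chosen so that the CIF equals the true rate.

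**1. Constant hazards over 30 days, true rate 10%.** Λe = 0.1096 and Λe + Λd = 0.1854. CIF = 0.591 × 0.1692 = 0.100. 1 − KM = 1 − exp(−0.1096) = 0.1038. Ratio 1.038.

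**2. Events within 7 days, deaths spread over 30, true rate 10%.** The death hazard by day 7 is 0.0758 × 7/30 = 0.0177. Λe = 0.1064 and the sum is 0.1241. CIF = 0.857 × 0.1167 = 0.100. 1 − KM = 1 − exp(−0.1064) = 0.1009. Ratio 1.009.

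**3. Upper bound.** The excess is largest if all deaths precede all events. The ratio is then 1/(1 − 0.073) = 1.079. At the other extreme, if no event follows an event-free death, the two estimates are equal.

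| True 30-day rate | KM reads: events within 7 days | KM reads: constant hazards | KM reads: upper bound | 95% CI half-width, N=1000 |
|---|---|---|---|---|
| 3% | 3.03% | 3.11% | 3.24% | 1.06 points |
| 5% | 5.04% | 5.19% | 5.39% | 1.35 points |
| 10% | 10.09% | 10.38% | 10.79% | 1.86 points |
| 20% | 20.17% | 20.74% | 21.57% | 2.48 points |

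The half-width is 1.96 × √(p(1 − p)/1000); for p = 0.10 this is 1.96 × 0.00949 = 1.86 points. Even at the bound, the excess (0.24, 0.39, 0.79 and 1.57 points) is below the half-width in every row.

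**4. Other mortality.** Over the 3.3% to 11% source range, the constant-hazard ratio runs from about 1.02 to 1.06. At 10% mortality it is about 1.05, with a bound of 1/0.90 = 1.111.

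**5. Which deaths compete.** The figures above count every death as competing. Under Protocol Appendix E.1, life-threatening bleeding includes fatal bleeding, stroke includes a deficit resulting in death, and major vascular complication includes injury leading to death. Those deaths are component events, so the true excess for these components is smaller. Kidney injury is defined only to day 7, so only deaths in that first week can compete and its excess is near nil.

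**6. Later time points.** If the rates were also reported at 3 years, with an assumed mortality of 20% to 40% and constant hazards, a true 10% would read 11.1% to 12.7% and a true 20% would read 22.2% to 25.2%.

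**The case against.** The strongest case against acting is that nothing turns on this. The objectives are descriptive, the primary endpoint is a binary mortality rate, and the composite already counts death. The excess is smaller than the sampling error, and overstating complications does not flatter the device. SAP 3.5 requires event counts, so with near-complete follow-up a reader can form a crude proportion close to the cumulative incidence. Kaplan-Meier is also the method in Protocol 2.7.4, and Protocol 5.7.2 gives comparability as a reason for following VARC-2.

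All of this stands, and it makes the point minor. It does not make the estimator match the endpoint. The discrepancy is systematic, so a larger sample would not remove it.

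A reader might infer that every component rate will be noticeably inflated. The documents do not support that. They give no event rates or timing, the larger excesses need deaths to come earlier than events, and some fatal events are themselves component events. A reader might also infer from the time points in SAP 3.5 that a larger bias at 1 to 3 years is planned. That does not follow: SAP 3.7.3.4 and 3.7.4.4 name only 30 days for these endpoints, and SAP 3.6.2 uses the later times for mortality.

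**Conclusion.** The point holds as a minor one. The SAP's rule makes the Kaplan-Meier rates of the components other than all-cause mortality, and of new pacemaker, at or above the 30-day proportions that the protocol asks for. At the planned 7.3% mortality, the relative excess is about 1% with events in the first 7 days, about 4% with constant hazards, and no more than 7.9%.

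The direction does not depend on the assumed event rates and timing; the size does. It also rests on treating every death as competing, which overstates the excess. The sample size and the mortality and composite results are untouched, and the evidence does not support a claim that the study's safety conclusions are distorted. The issue would matter more only if these rates were also reported at 1 to 3 years, which the SAP leaves unclear.

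**What to change.** In SAP 3.5, 3.7.3.4, 3.7.4.3 and 3.7.4.4, report each early-safety component other than all-cause mortality, and new permanent pacemaker, as Aalen-Johansen cumulative incidence at 30 days with a 95% confidence interval. Treat death without the component event as the competing event, so that a fatal stroke, bleed or vascular injury still counts as the component. Keep Kaplan-Meier for all-cause mortality and the composite. Show Kaplan-Meier component rates in a supplementary column for comparison with reports that used that method. State in SAP 3.5 which endpoints the 1, 2 and 3 year time points cover.

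Protocol 2.7.4 names Kaplan-Meier for time-to-event variables, so either align it or describe and justify the change in the final report, as Protocol 2.7 requires.

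The cost is a few sentences of text, a standard estimator and one extra table column. No new data are needed, and the sample size and primary test stay as they are.
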